During Phase 1, the dose of TPI 287 will be escalated in sequential dose cohorts (inter-cohort dose escalation). TPI 287 will be administered at an initial dose of 160 mg/m² as a 60-minute (\pm 10 minutes) intravenous (IV) infusion once every three weeks (i.e., 1 cycle = 21 days). If patients enrolled at this dose have no dose limiting toxicities (DLTs) within 21 days of receiving the first dose of study drug, additional patients will be enrolled in subsequent cohorts of 3 patients at 20 mg/m² increments (180 mg/m², 200 mg/m², 220 mg/m², etc.) to explore a maximum tolerated dose (MTD) on this schedule for this patient population. If patients experience DLT at the starting dose, one dose level below (Level -1) is also proposed.

If 1 out of 3 patients experiences a DLT within 21 days of receiving the first dose of study drug, an additional 3 patients will be enrolled in that cohort. If \geq 2 patients at

any dose level experience DLT within 21 days of receiving the first dose of study drug, the MTD will be the previous dose level tested.

The MTD determination will be based on the number of patients that experience DLTs within 21 days of receiving the first dose of study drug. DLTs will be considered to be any hematologic toxicity \geq Grade 3 within 21 days of receiving the first dose of study drug that does not recover within 3 weeks or any non-hematological toxicity \geq Grade 3 within 21 days of receiving the first dose of study drug that does not improve to Grade 1 or baseline within 3 weeks

Patients on the Phase 2 portion of the study will be enrolled at the MTD determined during Phase 1. Initially, 25 patients will be enrolled in the Phase 2 portion of the trial; if at least 5 patients are shown to have an objective response, an additional 26 patients will be enrolled.

Patients may continue treatment in the study at any dose until intracranial disease progression or death, unacceptable toxicity, withdrawal of consent, or discontinuation based on Investigator discretion. Patients will be followed for survival for up to 1 year after enrollment on the study.

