Intra-patient dose escalation will be allowed for patients with extracranial progressive disease as long as the response of intracranial disease is stable or better and there is no unacceptable toxicity. Only one dose escalation will be allowed per patient. The dose will be escalated to the next higher dose level (20 mg/m² increase); under the condition that this higher dose level was previously shown to be safe per the inter-cohort dose escalation criteria.

Table of Procedures and Assessments:

Event	Screen	Cycle 1			Cycle 2	Subsequent Cycles	Follow-Up Visit 28 ±2 days after last dose
		Day 1	Day 8	Day 15	Day 1		
Informed consent	X ²						
Medical & surgical history ^a	X ⁴						
Prior history and therapy for breast cancer ^b	X ⁴						
Demographics	X ⁴						
Physical examination ^c	X ⁴					X ³	X
Vital signs ^d	X ⁴	X				X ^{3, 6}	X
ECOG performance status	X ⁴	X ¹				X ¹	X
Laboratory Studies ^e	X ³	X ¹	X	X	X	X ¹	X
Urinalysis ^e	X ³						
Pregnancy test ^f	X ³						
Brain Gd-MRI ^g	X ²					X ⁷	X ³
Extracranial disease assessment ^g	X ²					X ⁷	X ³
Concomitant medications ^h	X ⁴	X ⁴				X	X
BSA calculation ⁱ		X ⁴				X ¹	
Administration of TPI 287 ^j		X ³			X ³	X ³	
AE monitoring ^k	X	X				X ¹	X
Survival ^l						X	X

Description/Definitions of Procedures and Assessments	Timing
a Complete medical and surgical history to include pertinent medical conditions and a careful history of all prior medical treatments	1 Prior to dosing with study drug within 7 days of each cycle unless otherwise specified
b Complete history of breast cancer to include date of diagnosis, histologic evidence of disease, dates of prior therapies (including surgery, radiation, chemotherapy) as well as date of documented recurrence/progression	2 Within 28 days of first dose of study drug
c Physical examination (including height and weight), noting all baseline abnormalities including neurologic exam	3 Within 14 (\pm 3 days) of first dose of study drug
d Temperature, pulse rate, blood pressure (sitting)	4 Within 7 days (\pm 3 days) days of dose of study drug

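### A patient taken off TPI 287 for good because of Grade 3-4 first-cycle toxicity that reverses within 3 weeks is not counted as a DLT, so the rule permits escalation past that dose

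*Combined protocol and SAP*

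**What the plan says.** The Proposed Treatment/Study Plan defines a DLT in two limbs.

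- Hematologic: toxicity at or above "Grade 3 within 21 days of receiving the first dose of study drug that does not recover within 3 weeks". The grade that counts as recovery is not stated.
- Non-hematological: toxicity at or above "Grade 3 within 21 days of receiving the first dose of study drug that does not improve to Grade 1 or baseline within 3 weeks".

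Only this count drives the dose decision, as the sentence "The MTD determination will be based on the number of patients that experience DLTs within 21 days of receiving the first dose of study drug" makes clear. The next cohort opens on the same basis: "If patients enrolled at this dose have no dose limiting toxicities (DLTs) within 21 days of receiving the first dose of study drug". One DLT among 3 patients adds 3 more at that level, and two or more make the previous level the MTD. Statistical Considerations restates the rule and adds no criterion for stopping treatment.

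The reasons for ending an individual patient's treatment are listed separately: "intracranial disease progression or death, unacceptable toxicity, withdrawal of consent, or discontinuation based on Investigator discretion". Nothing links them to the DLT count.

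The count has two further uses. It sets the Phase 2 dose: "Patients on the Phase 2 portion of the study will be enrolled at the MTD determined during Phase 1". It also decides which higher level is open to a patient with extracranial progression, "under the condition that this higher dose level was previously shown to be safe per the inter-cohort dose escalation criteria".

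**The concern.** An MTD is meant to be a dose that patients can go on receiving. Permanent withdrawal for severe drug toxicity is direct evidence against that, yet this definition does not see it if the toxicity reverses in time. Where such events occur, the counted DLT rate is lower than it would otherwise be, so the declared MTD can only stay the same or rise.

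That dose goes to up to 25 + 26 = 51 Phase 2 patients. The count also opens levels for intra-patient escalation, although there the plan adds safeguards: one escalation per patient, and only "as long as the response of intracranial disease is stable or better and there is no unacceptable toxicity". The Dose Levels table continues in 20 mg/m² steps with no stated ceiling, so the DLT definition is the main written brake on escalation.

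**Working it through.** **Which patients are affected.** All three conditions must hold: drug-related Grade 3-4 toxicity within 21 days of the first dose; reversal within 3 weeks (for non-hematological events, to Grade 1 or baseline); and permanent discontinuation because of that event. Deaths, events that do not reverse, and non-hematological events that improve only to Grade 2 from a lower baseline already count.

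**Inputs.** The cohort rule comes from the Proposed Treatment/Study Plan. The plan gives no operating figure for the escalation, so there is none to reproduce, and it gives no toxicity rates. I assume:

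- d = per-patient probability of a DLT as now defined, whether or not the patient continues;
- s = per-patient probability of an uncounted withdrawal (a patient with both kinds of event belongs to d);
- 1 DLT in 6 permits escalation. The plan implies this by stopping at two or more but does not say it.

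**Formula.** A level clears on 0/3, or on 1/3 followed by 0/3:

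P(clear) = (1−q)³ + 3q(1−q)²(1−q)³ = (1−q)³ + 3q(1−q)⁵

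As written, q = d. With withdrawals counted, q = d + s.

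**Why the difference is the chance of a changed decision.** Any set of patients that clears with withdrawals counted also clears as written, because dropping withdrawals from the count can only lower it. The difference is therefore the probability that a cleared level becomes a level that is not cleared.

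Example, d = 10% and s = 5%:

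- As written: 0.9³ + 3(0.1)(0.9⁵) = 0.729 + 0.177 = 0.906.
- With withdrawals counted: 0.85³ + 3(0.15)(0.85⁵) = 0.614 + 0.200 = 0.814.
- Difference: 0.092.

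| d | s | As written | Withdrawals counted | Difference |
|---|---|---|---|---|
| 0 | 2.5% | 1.000 | 0.993 | 0.007 |
| 0 | 5% | 1.000 | 0.973 | 0.027 |
| 7.5% | 2.5% | 0.944 | 0.906 | 0.038 |
| 5% | 5% | 0.973 | 0.906 | 0.067 |
| 0 | 10% | 1.000 | 0.906 | 0.094 |
| 10% | 2.5% | 0.906 | 0.862 | 0.044 |
| 10% | 5% | 0.906 | 0.814 | 0.092 |
| 15% | 5% | 0.814 | 0.709 | 0.105 |
| 10% | 10% | 0.906 | 0.709 | 0.198 |

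Differences are taken before rounding.

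**Without the 1-in-6 assumption.** If only 0/3 clears, P(clear) = (1−q)³. At d = 10% the value is 0.729 as written, against 0.670, 0.614 and 0.512 for s = 2.5%, 5% and 10%. The differences are 0.059, 0.115 and 0.217, so the picture is the same.

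**A related figure that should not be confused with this one.** With w = s/(1−d), the chance that a level clears as written with at least k uncounted withdrawals is

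(1−d)³ P(Bin(3,w) ≥ k) + 3d(1−d)⁵ P(Bin(5,w) ≥ k).

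At d = 10% and s = 2.5%, 5% and 10%, this is 8%, 16% and 30% for k = 1, and 0.3%, 1.1% and 4.2% for k = 2.

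**The case against.** The strongest reply is that this is a choice and not a mistake. The definition is explicit, the escalation rule is stated consistently in both places, and it ties dose limitation to toxicity that fails to reverse by a fixed time. Nothing in the plan promises that withdrawals count. That stands: no passage is contradicted or miscalculated, and the point is an improvement to the design.

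The background also points to low toxicity. The Rationale reports no DLT at 185 mg/m² every three weeks with Avastin in glioma patients, and no toxicity at 125 mg/m² given three weeks in four. The latter averages 125 × 3/4 × 3 = 281 mg/m² per 21 days. As single doses, however, Level 3 (200 mg/m²) and above exceed both, and the escalation exists to find where tolerability ends. The rates there are unknown in either direction.

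The supplied text is a protocol abstract, and Section 5 is not included. A rule there cannot be excluded, but the text cites that section only for drug administration, and the DLT definition shown reads as complete.

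The remedy makes part of the count depend on an open-label decision, and it adds a test of drug-relatedness that the existing limbs lack. In recurrent brain metastases, stopping for toxicity can be hard to separate from neurological decline. This stands as a cost; a dated, recorded decision limits it but does not remove it.

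A reader might infer that the plan forces escalation after such withdrawals. It does not: it permits escalation, and clinical judgment may still hold a cohort, although no supplied text provides for that. A reader might also take the 8%, 16% and 30% above as wrong decisions. They are not, because one withdrawal among 3 would only expand the cohort, and a third to nearly half of those levels would still clear.

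**Conclusion.** The point holds as a cheap improvement to a design choice. Following the stated rule can clear a level at which patients were permanently stopped for severe, drug-related, reversible toxicity.

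At d = 10%, the clearing decision for a level changes with probability of about 4%, 9% and 20% for s = 2.5%, 5% and 10%. At d = 0 with s of 5% or less, it is under 3%. Broadly, the effect is small when d + s is about 10% or less: at most 7 percentage points with s up to 5%, and 9 only if every such event is an uncounted withdrawal. It is material from about 20%, at 11 to 20 points in the cases shown.

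All of this rests on assumed rates. The documents do not support a claim that the declared MTD will be too high, or that severe first-cycle toxicity in general goes uncounted. They support only that this narrow group is missed and that the error has one direction. Confidence is medium because the rates are unknown.

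**What to change.** Add a third limb to the DLT definition: any drug-related toxicity of Grade 3 or higher (CTCAE version 4) arising within 21 days of the first dose for which TPI 287 is permanently discontinued, whether or not it recovers, with the decision and its reason recorded before any cycle 2 dose, by the end of the 3-week recovery window, and before the next cohort opens. Leave the two existing limbs unchanged. Reversible toxicity in patients who continue treatment stays uncounted, as now.

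The cost is one sentence and one dated data item. Footnote k to the Table of Procedures and Assessments already has drug-related toxicities followed to resolution, but the supplied text does not show that the reason for discontinuation is recorded. No new visit or committee is needed. The downsides are that the next cohort may occasionally wait, some levels may expand to 6 patients or fail sooner, the MTD may be lower, and the limb relies on the investigator's judgment of cause and of whether to stop.

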Protocol Abstract Page

A Phase 1/2 Open-Label Study of TPI 287 in Patients with Breast Cancer Metastatic to the Brain 2010-0198

Core Protocol Information

Study Chairman:	[name]
Department:	Breast Medical Oncology
[contact]
Unit:	1354
Full Title:	A Phase 1/2 Open-Label Study of TPI 287 in Patients with Breast Cancer Metastatic to the Brain
Protocol Phase:	Phase II
Version Status:	Terminated 04/18/2017
Version:	11
Document Status:	Final

Abstract

Objectives:

Primary objective (Phase 1)

To evaluate the maximum tolerated dose (MTD) and safety of TPI 287 administered once every three weeks in patients with refractory or recurrent breast cancer metastatic to the brain

Primary objective (Phase 2):

To estimate the efficacy of TPI 287 by assessing the overall response rate [ORR (CR + PR)] of recurrent brain metastases using the McDonald Criteria.

Secondary objectives (Phase 1 and 2):

- a. To evaluate response duration of breast brain metastases on TPI 287
- b. To evaluate rate and duration of the clinical benefit (CR+PR+SD)
- c. To assess activity of TPI 287 on extracranial metastatic disease
- d. To measure median progression free and overall survival of patients with metastatic breast cancer treated with TPI 287

Rationale: (Be as concise as possible)

The current study proposes to examine a novel microtubule inhibitor TPI 287 that has shown potency and efficacy in a number of taxane sensitive and resistant tumors in

both preclinical and clinical studies. TPI 287 has also been shown to be very well tolerated and exhibits limited myelosuppression at the currently employed doses. It has also been shown that IV TPI 287 can penetrate the brain parenchyma to reach pharmacologically and clinically relevant levels, which suggests that breast cancers metastatic to the brain would be an appropriate target for therapy. There is a significant amount of human safety data for TPI 287 with over 100 adult patients and now 5 pediatric patients who have received drug in prior clinical trials to adequately assess the safety of the clinical trial and the dosing regimen for TPI 287 planned.

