e Complete blood count, including RBC, MCV, MCH, MCHC, hemoglobin, hematocrit, WBC with differential, and platelet count (WBC with differential and platelets will be collected weekly for 1 st cycle and within 7 days of each subsequent cycles); additional labs to be obtained at these time include sodium, potassium, chloride, bicarbonate, calcium, glucose, BUN, creatinine, albumin, total protein, alkaline phosphatase, total bilirubin, ALT, AST; Dipstick determinations of urinary protein, glucose, ketones, hemoglobin, and bilirubin, but only for the first three cycles and/or if clinical indicated. Patients who are taking coumadin (warfarin) will have PT, PTT, and INR prior to each cycle of treatment. Patients who have 2+ or greater hemoglobin or protein on a spot urine must have a microscopic examination performed. Urine exam is done only at screening.	5 Prior to dosing as interim update (only note changes from prior record). To be obtained within \pm 3 days.
f For females of childbearing potential only, may be based on serum or urine testing	6 Prior to dosing with study drug and immediately following 60 minute infusion
g Brain Gd-MRI must be obtained as per protocol. Extracranial disease assessments may include CT/MRI scans of chest, abdomen, pelvis as well as bone scans, and as per standard of care otherwise indicated by treating physician. All disease assessments will be performed when clinically indicated.	7 Within 7 days prior to odd numbered cycles
h All medications/therapies used within 30 days prior to first dose of study drug	8 If scan has not been obtained within previous 2 cycles
i If weight fluctuates \pm 10% from prior measurement, new BSA will be used to calculate next dose	9 Within (\pm 1 day)
j One hour IV infusion of TPI 287 Injection on day 1 every 21 days. See Section 5 for Study Drug Administration.	
k All drug-related toxicities must be followed for resolution. Patients are to be followed for up to 30 days (\pm 5 days) after last drug administration for adverse events, regardless of causal relationship.	
l Data will be collected every 3 months from the time the patient is off-treatment up to a period of 1 year from the patient's date of enrollment	

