* Note that the timing of assessments may be varied by reasonable adjustments to the times indicated for scheduling or logistical issues. Patients whose on study laboratory tests were done > 7 days prior to starting treatment and whose clinical condition has changed between the time of these tests and the initiation of treatment will have a repeat chemistry panel prior to the start of treatment.

Dose Levels:

Level	Dose of TPI 287 (mg/m²)
Level - 1	140
Starting dose/Level 1	160
Level 2	180
Level 3	200
Additional dose level increases in 20 mg/m² increments	

CTCAE version 4 will be utilized in this protocol.

Study Enrollment:

The study population for this research will consist of participants from:

Only at MDACC

Estimated Accrual:

Total Accrual at MDACC: 69
 Estimated monthly accrual at MDACC: 0-1

Accrual Comments:

All patients will be accrued MD Anderson Cancer Center

Is this an NCI-Cancer Therapy Evaluation Protocol (CTEP)? No

Is this an NCI-Division of Cancer Prevention Protocol (DCP)? No

Statistical Considerations:

This is an open label, Phase 1/2, exploratory trial evaluating the efficacy and safety of TPI 287 in patients with refractory or recurrent brain metastases from breast cancer.

The primary objective of the Phase 1 portion of the study is to determine the MTD of TPI 287 and in the Phase 2 portion of the study whether TPI 287 can provide clinical benefit for patients with metastatic breast cancer to the brain following failure of prior therapy, as measured by overall response rate.

TPI 287 will be administered intravenously at an initial dose of 160 mg/m² once every three weeks. Dose escalation will continue in cohorts of 3 patients who will receive increasing doses until 1 out of 3 experience a dose limiting toxicity (DLT) at which time an additional 3 patients will be added at that dose. If ≥ 2 patients experience a DLT, the MTD will be considered the prior dose level. Dose levels will be 160 mg/m², 180 mg/m², 200 mg/m² and then increased in 20 mg/m² increments until the MTD is reached.

Once the MTD has been reached an initial cohort of 25 patients will be enrolled; if at least 5 patients are shown to have an objective response, an additional 26 patients will be enrolled.

The following data sets will be used in this study:

- All enrolled and eligible subjects (ITT) population: All eligible subjects who signed the informed consent form.

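### Does footnote g undo the odd-cycle scan schedule, and does the one-year survival cap defeat the median OS objective?

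*Combined protocol and SAP*

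**What the plan says.** **Scan schedule.** In the Table of Procedures and Assessments, the brain Gd-MRI and extracranial rows carry identical marks: timing 2 at screening, timing 7 in subsequent cycles, timing 3 at the follow-up visit. Timing 7 reads "Within 7 days prior to odd numbered cycles". A cycle is 21 days, so the interval is 2 × 21 = 42 days.

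Footnote g applies to both rows and has three parts:
- For the brain: "Brain Gd-MRI must be obtained as per protocol".
- For extracranial disease: a list of permitted imaging, with a clause that leaves it to standard of care or the treating physician.
- For both: "All disease assessments will be performed when clinically indicated".

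The note under the table adds that the "timing of assessments may be varied by reasonable adjustments to the times indicated for scheduling or logistical issues".

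**Where extracranial findings are used.** Secondary objective c is "To assess activity of TPI 287 on extracranial metastatic disease". The Proposed Treatment/Study Plan also says: "Intra-patient dose escalation will be allowed for patients with extracranial progressive disease".

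**Survival.** Secondary objective d is "To measure median progression free and overall survival of patients with metastatic breast cancer treated with TPI 287". The Proposed Treatment/Study Plan says: "Patients will be followed for survival for up to 1 year after enrollment on the study". Footnote l agrees: data are collected every 3 months once the patient is off treatment, up to one year from enrollment. No expected survival, landmark rate or rule for an unreached median is given.

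**The concern.** The last sentence of footnote g covers all disease assessments and does not say that indicated scans are extra. If it replaced the schedule, the date on which extracranial progression is found would depend on when each physician ordered a scan. Extracranial activity (objective c) and any extracranial part of progression-free survival (objective d) would then rest on irregular assessment, with no control arm to share the error. Detection of the condition for the one permitted intra-patient escalation would vary in the same way. The note under the table does not settle the matter, because it concerns only scheduling and logistics.

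On survival, a median cannot be estimated unless about half the patients die within the follow-up window. With a 12-month cap and no stated expectation, objective d might name a quantity that the trial cannot deliver, or can deliver only without an upper confidence limit.

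**Working it through.** **1. Footnote g against the table**

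Take the replacement reading first. The sentence makes no distinction between brain and extracranial scans, so it would have to replace the schedule for both. For the brain that contradicts the mandatory sentence in the same footnote. It would also leave timing 7 with no function in either row. Timing 8, which concerns patients with no scan in the preceding two cycles, presupposes a two-cycle interval too. (In the extracted text timing 8 is attached to no cell, possibly through extraction, so it is only supporting evidence.)

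Now take the additive reading: scans every 42 days, plus any that symptoms call for. Timings 7 and 8, the brain MRI sentence and the logistics note all keep their meaning. The standard-of-care clause can be read as governing which imaging is used and what is done beyond the table. No effect size can be computed for this part.

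**2. Median survival under a 12-month cap**

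The plan states no survival figure to reproduce. Its two-stage design supplies the sample sizes. With 25 patients and continuation on 5 or more responses, the chance of stopping at stage 1 when the response rate is 15% is 1 − P(Bin(25, 0.15) ≥ 5) = 68.2%, against the stated 68%. Both n = 25 and n = 51 are therefore realistic.

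Assumptions, not from the documents: exponential survival, every patient followed to death or month 12, Phase 2 patients only.

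- Probability of death by month 12: p = 1 − 0.5^(12/m), where m is the true median in months.
- Median reached: P(Bin(25, p) ≥ 13) or P(Bin(51, p) ≥ 26).
- Upper 95% limit of the median reached (log-log or order-statistic interval): P(Bin(25, p) ≥ 18) or P(Bin(51, p) ≥ 33).

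| True median (months) | p | Median reached, n=25 | Median reached, n=51 | Upper limit reached, n=25 | Upper limit reached, n=51 |
|---|---|---|---|---|---|
| 4 | 0.875 | about 100% | about 100% | 99% | about 100% |
| 6 | 0.750 | 99.7% | >99.9% | 72.7% | 96.5% |
| 8 | 0.646 | 93.5% | 98.4% | 29.3% | 56.0% |
| 10 | 0.565 | 74.4% | 82.5% | 8.4% | 14.8% |
| 12 | 0.500 | 50% | 50% | 2.2% | 2.4% |

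With log-transformed limits the thresholds rise to 19 and 34 deaths, and at 8 months the upper limit is reached less often (16.4% and 44.4%). In simulation, losing 10 to 20% of patients by month 12 moved these probabilities by only a few points.

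The median itself is at appreciable risk only from about 10 months upward. The large failure rates at 8 months belong to the upper limit, which objective d does not ask for.

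**3. What landmark rates would add**

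Under the same assumptions, exact 95% intervals at a true median of 8 months have expected half-widths of 19.8 points (6-month rate) and 19.3 points (12-month rate) at n = 25, and 14.0 and 13.6 points at n = 51. A Kaplan–Meier curve drawn for the median shows these rates anyway. Nor is a complete 12-month rate free: under footnote l a patient off treatment at month 2 is contacted at months 5, 8 and 11, and no month-12 contact is stated.

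**The case for a change.** The best case for a change is that both remedies are cheap. One sentence would settle footnote g without adding a scan. The imbalance in the footnote is real: the brain has a mandatory sentence, while extracranial disease has a permissive one that defers to the treating physician. On survival, stopping at 25 patients is likely if the drug is inactive, and at that size the upper limit is missing in about 27% of trials even at a true median of 6 months. Nothing in the documents rules out 8 to 10 months.

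Some of this stands. Footnote g is loosely worded, and its standard-of-care clause is looser than the sentence quoted against it. But the table fixes the extracranial schedule as it fixes the brain schedule, and a site that follows the table gets sound data. The text available is also a protocol abstract: footnote j points to a Section 5 that is not included, so fuller rules may exist.

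The survival probabilities stand as arithmetic. What they show depends on an assumed median. Statistical Considerations describes heavily pre-treated patients whose alternative is best supportive or hospice care. That suggests shorter survival, where the cap does little harm to the median, but it does not prove it.

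**Conclusion.** No change to the plan follows from either point.

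Footnote g is a drafting looseness that readers of the table will resolve sensibly. The additive reading is the only one consistent with the brain MRI sentence and with timing 7 on both rows. The primary response endpoint is largely protected in any case, the remaining exposure is confined to secondary uses of extracranial scans, and no size can be put on it.

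The one-year cap is stated consistently and is a fair trade-off in an exploratory single-arm trial. If the true median survival is 8 months or less, the median is reached in at least 93.5% of trials at n = 25 and 98.4% at n = 51. At 10 months this falls to about 74% and 82%, and at 12 months to half. These figures assume exponential survival and complete follow-up, and the range of medians is an assumption because the documents give none. If the median is not reached, reporting that, with the survival curve, is a correct answer to objective d. Prespecifying 6- and 12-month rates would be a preference, not the correction of a wrong result.

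### Tumour scans are scheduled by cycle number with no calendar interval, so a delayed dose moves the scan and recorded progression dates come to depend on dosing as well as on tumour growth

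*Combined protocol and SAP*

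**What the plan says.** In the Table of Procedures and Assessments, on-treatment brain Gd-MRI and extracranial disease assessment carry timing note 7: "Within 7 days prior to odd numbered cycles". Timing note 8 also counts in cycles: "If scan has not been obtained within previous 2 cycles". Footnote j sets dosing as "One hour IV infusion of TPI 287 Injection on day 1 every 21 days" and refers to a Section 5 for administration, which is not in the supplied text.

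Two statements loosen the schedule. Footnote g says "All disease assessments will be performed when clinically indicated", and the note under the table says that "the timing of assessments may be varied by reasonable adjustments to the times indicated for scheduling or logistical issues". Neither sets an interval or says that a scan keeps its date when a dose is late.

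Three secondary endpoints depend on the recorded date of progression. Objective (a) reads "To evaluate response duration of breast brain metastases on TPI 287"; objective (b) includes the duration of clinical benefit; objective (d) includes median PFS. The primary Phase 2 endpoint is the overall response rate.

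**The concern.** Cycle-based and calendar-based scanning agree only while dosing is on schedule. Cycle 3 is due 42 days after the first dose, so the first on-treatment scan falls on days 36 to 42. If cycle 2 or cycle 3 starts 3 weeks late, the scan moves to days 57 to 63, and a patient whose disease grew silently in the meantime is recorded as progressing up to 3 weeks later than under a fixed schedule.

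Late cycles are plausible. The DLT definition considers toxicity of Grade 3 or higher "that does not recover within 3 weeks", so slow recovery is at least contemplated. If toxicity is the cause of the delay, the date of progression reflects tolerability as well as tumour control. In a single-arm trial PFS and the durations are read at face value, with no control group to show the effect.

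**Working it through.** **The plan's own figures.** The documents give none for scan timing, PFS or duration. Their only operating characteristics belong to the two-stage response rule: 25 + 26 patients, continue with at least 5 of 25, success with at least 11 of 51. The exact binomial calculation reproduces them.

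- Early termination at 15%: P(X1 ≤ 4) = 68.2% (stated 68%).
- Alpha at 15%: Σ over x1 ≥ 5 of P(X1 = x1)·P(X2 ≥ 11 − x1) = 10.7% (stated 11%).
- The same sum at 30% is 87.6%, so beta = 12.4% (stated 12%).

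These depend on stage sizes, cut-offs and response rates only. No scan date enters.

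**Inputs for the timing check.** From the documents: 21-day cycles and scans before odd-numbered cycles, so a scan interval of 2 × 21 = 42 days. Assumed: exponential time to progression with median m = 60 or 90 days; one delay of d = 7, 14 or 21 days before the first scan; 20 or 40% of patients delayed; no symptom-triggered scans. Scans are placed at the late edge of the window.

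**Formula.** Progression is recorded at the first scan on or after it occurs. Scans fall on days 42, 84, 126, … without a delay, and on 42 + d, 84 + d, … with one. A patient who progresses within d days after an undelayed scan date (day 42 or later) is recorded 42 − d days *earlier* under the delayed schedule. Every other patient is recorded d days *later*. With λ = ln 2 / m and q = exp(−42λ), the share recorded earlier is

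s = q(1 − exp(−λd)) / (1 − q),

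and the mean shift is d(1 − s) − (42 − d)s = d − 42s.

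For m = 60, q = 0.6156; for m = 90, q = 0.7236. Example, m = 60 and d = 21: s = 0.6156 × 0.2154 / 0.3844 = 0.345, and the shift is 21 − 42 × 0.345 = 6.5 days.

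| Median m | Delay d | Recorded earlier (s) | Mean shift, delayed patients | Cohort mean, 20% / 40% delayed | Recorded median, no delay → all delayed |
|---|---|---|---|---|---|
| 60 | 7 | 12% | +1.8 days | +0.4 / +0.7 | 84 → 91 |
| 60 | 14 | 24% | +4.0 days | +0.8 / +1.6 | 84 → 98 |
| 60 | 21 | 34% | +6.5 days | +1.3 / +2.6 | 84 → 63 |
| 90 | 7 | 14% | +1.2 days | +0.2 / +0.5 | 126 → 91 |
| 90 | 14 | 27% | +2.8 days | +0.6 / +1.1 | 126 → 98 |
| 90 | 21 | 39% | +4.6 days | +0.9 / +1.8 | 126 → 105 |

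The mean shift is positive in every row. Patients who progress before day 42 (1 − q = 38% and 28%) are all recorded the full d days late.

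**Median PFS.** The recorded median can fall only on a scan date, so it moves in jumps. Among delayed patients it is longer in two rows and shorter in four. For the whole cohort it is unchanged in 11 of the 12 combinations of median, delay and share, and shorter in the other (m = 90, d = 21, 40% delayed: 126 → 105 days).

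**Repeated delays.** A simulation of 400,000 patients with assumed medians of 6 to 18 weeks gives a mean shift of +0.5 to +0.6 weeks for a 1-week delay in every two-cycle block, and +1.6 to +1.9 weeks for a 3-week delay in every block.

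**Response duration.** Take true onset at week 4, true progression at week 17 and a 3-week delay. A delay after the response scan changes the recorded duration from 12 to 15 weeks (scans at 6 and 21 instead of 6 and 18). A delay before the first scan leaves it at 12 weeks (9 and 21), because both dates move. With true progression at week 20, the early delay shortens it from 18 weeks (6 to 24) to 12 (9 to 21).

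**The case against.** The strongest objection concerns direction. A reader might infer that cycle-based scanning always lengthens recorded PFS and so flatters the drug. The calculation does not support this: 12 to 39% of delayed patients are recorded earlier, and the endpoint named in the protocol is the median, which in these scenarios is mostly unchanged for the cohort and never longer. Nor does response duration lengthen generally; it does so mainly when the delay follows documented response. This part stands, and the claim is limited to the mean.

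Second, the delay is inferred. The 3-week recovery period belongs to the DLT definition and is not a dosing rule; the Rationale describes the drug as well tolerated with little marrow suppression; and Section 5 cannot be seen. This stands as a limit on size. It does not remove the gap, because the schedule in the table has no calendar backstop whatever the frequency of delays.

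Third, clinically indicated assessments can catch symptomatic progression, and the definition of progression in inclusion criterion 2 includes clinical worsening. That makes the mean shifts for a single delay upper-end values. It does not help with silent growth on MRI, and the permitted timing adjustments do not require routine scans to stay on the calendar.

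Fourth, the trial is exploratory and single-arm, and the plan states no target or test for PFS or the durations. There is no between-arm bias and no decision rule is touched. The ordinary overshoot of about 3 weeks from 6-weekly scanning is larger than this effect and remains after the fix. All of this stands, and it is why the severity is low.

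**Conclusion.** The point holds in a bounded form. Routine scans are tied to cycle number with no calendar interval, so a delayed dose moves the scheduled scan, and recorded progression dates then depend partly on dosing. With one 7 to 21 day delay before the first scan, the mean is about 1 to 6.5 days later in delayed patients and under 3 days later for the cohort at 20 to 40% delayed. This rests on assumed exponential progression with median 60 to 90 days and no symptom-triggered scans; the documents supply none of these values and no delay frequency. The effect is confined to PFS, response duration and benefit duration. It gives no ground for calling the reported median PFS inflated or for doubting the stated error rates of the response-rate design. Low severity, worth a one-line correction.

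**What to change.** Replace timing note 7 with: every 6 weeks (42 days, -7 days) from Cycle 1 Day 1 until progression, regardless of dose delays or cycle number. Patients dosed on schedule keep the present timing, and no dosing rule changes. The extra shift from dose delay becomes zero by construction. The cost is one line in the table and, after a delay, an occasional scan that does not coincide with a dosing visit.
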